4.1 Randomisation and Blinding

OIT outcomes have been reported to be affected by a range of variables, including age, baseline egg-specific IgE, baseline reaction threshold and the presence of asthma (10). It is therefore essential to maintain balance between treatment groups with respect to these predictors. However, stratified randomisation using several variables is not effective in small trials. Minimisation is a valid alternative to ordinary randomisation, and has the advantage that there will be only minor differences between groups in baseline variables which are used in the allocation process (11). With minimisation, the treatment allocated to the next participant enrolled in the trial depends on the characteristics of those participants already enrolled, with an element of weighted randomisation – typically 80% chance – of each participant getting the allocation that minimises any imbalance. Randomisation with 2:1 allocation ratio will be performed using an online free, open-source, desktop minimization program with a random element using a weighting probability of 0.8 (MinimPy Program 0.3).

Baseline variables included in the minimisation will be:

- Age (<5, \geq 5 years)
- Egg-specific serum IgE (<10 kU/L, \geq 10 kU/L)
- Asthma on inhaled corticosteroids (No, Yes)

This is an open label study and blinding will not be performed.

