4.3.2.9 Quality of Life Assessments

The impact of OIT on participants' health-related quality of life (HRQL) will be assessed both from parents' and participants' perspective using disease-specific validated "food-allergy quality of life questionnaire" (FAQL-Q) in its parental, child and teenager forms. The FAQLQ-PF (parent form) will be administered to all parents; FAQLQ-CF (child form) administered to patients age 8-12 years at commencement of study; FAQLQ-TF (teenager form) administered to patients age 13-18 years at commencement of study. To ensure the ability to compare responses consistently during the 12 months of OIT, children who are age 12 at study commencement will be asked to complete the Teenage version unless there are difficulties with comprehension which preclude this.

These will be performed for subjects in the active arm at the following points during the study:

- i. baseline, at screening (TS).
- ii. prior to cookie initial escalation (T1C).
- iii. prior to pancake initial escalation (T1P/ T2P)
- iv. prior to the DS FC (T3).
- v. prior to SU FC (T4).

Subjects in the control arm will be assessed at baseline (TS) and prior to DS FC (T3).

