9 SAMPLE SIZE AND STATISTICAL METHODS

9.1 Determination of Sample Size

The incidence of natural resolution of egg allergy over 12 month period is about 15% (4),(10). The efficacy for desensitisation using raw/cooked eggs is about 80% (ranging between 55% -100%) whilst that for OIT using baked egg products is about 50%. As there are no prior studies using pancake to desensitise egg-allergic patients, we are estimating the efficacy to be in between that of raw/cooked eggs and baked eggs, at about 65%. We plan to recruit 33 egg-allergic children to the study, who will be randomised 2:1 to active (n=22) or control (n=11) groups. This will allow us to detect a difference in rates of desensitisation of 50%, with 80% power using a two-sided significance level of 0.05, whilst allowing for a 30% attrition rate. Sample size calculation was performed using PASS 14 (Power Analysis and Sample Size Software (2015). NCSS, LLC. Kaysville, Utah, USA, [ncss.com/software/pass.](http://ncss.com/software/pass/)).

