9.2.2 Analysis of Secondary Outcomes

The following secondary analyses will be performed:

- Proportion of subjects who tolerate 4443mg or more of egg protein in the active and control groups, following cessation of all egg intake for 6 weeks (sustained unresponsiveness), using a two-sided Fisher's exact test.
- The incidence of adverse events experienced between active and control groups. Statistical differences will be determined using two-sided Fisher's exact test for proportions; non parametric tests for graded reactions. Logistic regression will be used to assess the association of age, gender, asthma status and prior history of anaphylaxis with incidence of adverse events.
- Completion rates in the active and control groups will be compared using a two-sided Fisher's exact test.
- Change in quality of life assessments before and after OIT, as assessed by FAQL-Q in children, teenagers and their parents – between the active and control groups using two independent sample t test (or Mann-Whitney U test if normality assumption is not tenable). The changes within each group will be assessed using paired t test (or Wilcoxon signed rank test if normality assumption is not tenable).
- Immunological outcome measures pre- and post- of OIT, using paired t test (or Wilcoxon signed rank test if normality assumption is not tenable) within each group.

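### Adjusting the between-arm quality-of-life comparison for the screening score would usually be more precise than the planned test on change scores, at almost no cost

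*Combined protocol and SAP*

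**What the plan says.** Quality of life is the fourth secondary objective (section 2.3). Section 9.2.2 defines the outcome as "Change in quality of life assessments before and after OIT, as assessed by FAQL-Q in children, teenagers and their parents" and compares it "between the active and control groups using two independent sample t test (or Mann-Whitney U test if normality assumption is not tenable". Paired tests within each arm are added. No covariate is named; the only regression model in section 9 is a logistic model for adverse events.

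The baseline score exists in both arms. Section 4.3.1 lists the questionnaire among the TS procedures, and randomisation follows once eligibility is met. Section 4.3.2.9 schedules the active arm at TS, T1C, T1P/T2P, T3 and T4, and states: "Subjects in the control arm will be assessed at baseline (TS) and prior to DS FC (T3". The parent form goes to all parents. The child and teenager forms depend on age, for example "FAQLQ-CF (child form) administered to patients age 8-12 years at commencement of study".

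Section 9.1 has children "randomised 2:1 to active (n=22) or control (n=11) groups". Section 4.1 says that with minimisation "there will be only minor differences between groups in baseline variables which are used in the allocation process". Those variables are age, egg-specific IgE and asthma on inhaled corticosteroids. FAQL-Q is not among them.

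**The concern.** A change score subtracts the whole of the baseline value. That is the best use of baseline only if the T3 score rises one for one with the TS score. If the slope is below 1, subtraction removes too much: it adds noise, and the arm that happens to start worse tends to show the larger improvement. With 11 controls, and with FAQL-Q outside the minimisation, a noticeable chance difference in baseline scores is quite possible. At stake are the width of the confidence interval for the quality-of-life effect and how far the estimate depends on the luck of allocation.

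**Working it through.** **Inputs.** From the documents: 22 active and 11 control (9.1), and the sample size is set "with 80% power using a two-sided significance level of 0.05, whilst allowing for a 30% attrition rate". Applying 30% to each arm gives 22 x 0.7 = 15.4 and 11 x 0.7 = 7.7, so about 15 v 8. Assumed, because the documents do not give them: rho from 0.3 to 0.9, equal SDs at TS and T3 (relaxed in step 4), and the size of the true effect.

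**The plan's own figure.** No sample size, SD or power is stated for quality of life. The total of 33 is for desensitisation, 65% v 15%. The unpooled z formula gives (1.960 + 0.842)^2 x (0.15 x 0.85 + 0.65 x 0.35/2)/0.50^2 = 7.57 controls, 22.7 in total, and 22.7/0.7 = 32.5, so 33. It supplies only the arm sizes here.

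**Step 1: variances.** With unit SDs:

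- Change score: 2(1 - rho) x (1/n1 + 1/n0).
- ANCOVA: (1 - rho^2) x (1/n1 + 1/n0) x (1 + 1/(N - 4)). The last factor is the average cost of estimating the slope.
- Ratio: (1 + rho)/2 x (1 + 1/(N - 4)).

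The factor is 1 + 1/29 = 1.034 at N = 33 and 1 + 1/19 = 1.053 at N = 23. For rho 0.5 and N = 33: 0.75 x 1.034 = 0.78.

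**Step 2: results.** The detectable difference is at 80% power, two-sided 0.05, from the noncentral t distribution. The last column is simulated (20,000 trials per setting, normal scores) for an assumed true effect of 0.8 SD.

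| rho | Variance ratio, 22 v 11 | Variance ratio, 15 v 8 | Detectable difference in SD, 22 v 11: change, ANCOVA | Power for 0.8 SD, 22 v 11: change, ANCOVA |
|---|---|---|---|---|
| 0.3 | 0.67 | 0.68 | 1.26, 1.04 | 42%, 58% |
| 0.5 | 0.78 | 0.79 | 1.07, 0.94 | 56%, 67% |
| 0.7 | 0.88 | 0.90 | 0.83, 0.78 | 77%, 83% |
| 0.9 | 0.98 | 1.00 | 0.48, 0.47 | 99.7%, 99.7% |

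**Step 3: baseline imbalance.** The chance difference in baseline means has SD sqrt(1/22 + 1/11) = 0.37 of a score SD at 22 v 11, and sqrt(1/15 + 1/8) = 0.44 at 15 v 8. Given an observed difference D, the change-score estimate is shifted by -(1 - slope) x D. With equal SDs the slope equals rho, so a typical D of 0.37 at rho 0.5 shifts the estimate by 0.5 x 0.37, about 0.18 SD. The simulated shift per unit of D was about -0.70, -0.50, -0.30 and -0.10 at the four values of rho. For ANCOVA it was about 0.

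**Step 4: unequal SDs.** Let k = SD(T3)/SD(TS), so the slope is rho x k. With TS SD of 1, the change variance is k^2 + 1 - 2 x rho x k and the ANCOVA residual variance is k^2 x (1 - rho^2). The two differ by (1 - slope)^2, so the large-sample gain depends on how far the slope is from 1. Example with assumed values rho 0.7 and k 1.3: slope 0.91; change variance 1.69 + 1 - 1.82 = 0.87; ANCOVA 1.69 x 0.51 = 0.862. After the small-sample factor the ratio is about 1.02 at 22 v 11 and 1.04 at 15 v 8, so no gain.

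**Step 5: validity.** With no true effect, both methods rejected in about 5% of simulated trials, and both were unbiased on average.

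**The case against.** The strongest reply is that the planned test is prespecified, legitimate and already uses the baseline. That stands. A reader might infer that the test is biased or has the wrong error rate; step 5 shows neither. A reader might also say that a change score always over-corrects unless rho is 1; that holds only with equal SDs, and step 4 shows that the slope is what matters.

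Three further inferences go beyond the documents:

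- That the time points are undefined. "Change in quality of life assessments before and after OIT" is loose, but controls have only TS and T3, so TS to T3 is the only between-arm change available. Naming it is a clarification.
- That the child and teenager forms cannot support a test. No age distribution within 2 to 15 years is given. A split such as 4 v 2, where the smallest two-sided Mann-Whitney p is 2/15 = 0.133, is only hypothetical.
- That adjustment solves the quality-of-life analysis. Section 4.3.2.6 gives active children T3 after at least 16 weeks of maintenance, and withdrawn children complete the questionnaire only if willing (4.4.2). Missing T3 scores affect both methods and could matter more than the choice between them.

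It is also fair that the plan has a fallback for non-normal data, which a bare ANCOVA would lose, and that the outcome is secondary with no power claimed.

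What remains is that the same data can generally be analysed more precisely, without dependence on chance imbalance in the baseline score.

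**Conclusion.** The point holds as an efficiency improvement, not as an error. With equal SDs, ANCOVA cuts the variance of the arm difference by about 33%, 22%, 12% and 2% at rho 0.3, 0.5, 0.7 and 0.9 for 22 v 11. At 15 v 8 the gain is nil by rho 0.9. The gain shrinks or disappears if scores are more spread out at T3 than at TS. Because the documents give neither SDs nor rho, the range is what can be defended, not a single figure. The primary outcome, the safety analyses and the type I error are not affected.

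**What to change.** In section 9.2.2, replace the between-arm quality-of-life test with an ANCOVA:

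- T3 score as outcome, arm as factor and TS score as covariate, with TS to T3 stated as the interval in both arms.
- Fit it at least for the parent form, and for the child and teenager forms where numbers allow.
- Report the adjusted difference with its 95% CI.
- Keep a fallback if residuals are clearly non-normal, for example a rank-based ANCOVA, or the planned Mann-Whitney test as a sensitivity analysis.

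The cost is a change of wording and one degree of freedom. No new assessment is needed. If the slope is in fact 1, the average variance penalty is 1/29, about 3%, with all 33 children, or 1/19, about 5%, with 23. That is roughly 2% to 3% on the standard error.

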1.2.2 Rationale for Study Design

This is a randomised controlled study exploring the efficacy, safety and feasibility of a novel form of egg OIT using pancakes to induce desensitisation and sustained unresponsiveness in egg allergic patients. The control group receiving current standard care of egg avoidance, will be used to control for the incidence of natural resolution of egg allergy over the study period. Safety of OIT and its impact on quality of life measures will also be compared against the risk of accidental reactions among controls who continue strict egg avoidance. Allocation ratio of 2:1 (active:control) allows for more patients to be given a chance to receive OIT.

This is an open label study as we wish to assess a pragmatic approach to OIT with home preparation of pancakes and cookies using store bought eggs, in which blinding will not be feasible nor practical.

Subjects randomised to the active arm will undergo an open baked egg food challenge (FC) to determine their baseline baked egg tolerance. Baked egg tolerant (BET) patients will directly undergo OIT using pancakes. Baked egg reactive (BER) patients will commence OIT with baked egg (cookies), to first achieve desensitisation to baked egg before transitioning to pancakes. Desensitisation will be assessed by an open cooked egg FC at the end of treatment while SU will be assessed by an open cooked egg FC after stopping OIT for approximately 6 weeks.

Updosings for cookies will be done at home under the guidance of the study team based on the safety profile of other home-based baked egg OIT protocols (7),(8). Updosings for pancakes will be performed in the hospital as this has not been evaluated previously.

Subjects randomised to the control arm will continue strict egg avoidance and undergo an open cooked egg FC between 12 and 18 months.

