2.3 Secondary Objectives

1. To evaluate the efficacy of pancake OIT in inducing sustained unresponsiveness in egg-allergic children.
2. To evaluate the safety and feasibility of using pancake as OIT for egg-allergic children.
3. To compare immunological outcomes (skin prick test to egg white, serum IgE to egg white, ovomucoid, ovalbumin) at baseline and end of OIT program.
4. To assess the impact of OIT on health-related quality of life.
5. To compare the immune cell profiles at baseline and end of OIT program.
6. To identify the mechanistic basis of resistance, desensitisation and SU to OIT.

2.4 Potential Risks and Benefits:

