4.3.2.6 Desensitisation (DS) Open Food Challenge (T3)

All participants who have completed at least 16 weeks of maintenance pancake OIT (Table 5 Step 7) will undergo an open cooked egg challenge at the end of treatment (T3) to assess for desensitisation. This is subjected to a total OIT duration (from initial escalation to exit challenge) of a minimum 12 months and maximum 18 months. All control subjects will undergo an open cooked egg challenge between 12 and 18 months (T3).

Desensitisation Open Food Challenge to Cooked Egg		
Dose	Egg Protein (mg)	Equivalent serving of cooked egg (g)
1	3	0.02
2	10	0.08
3	30	0.24
4	100	0.8
5	300	2.4
6	1000	8
7	3000	24
Cumulative dose		35.54

Table 7: Dosing protocol for DS Open FC to cooked egg

Successful desensitisation is defined as passing the FC to cooked egg, tolerating 4443mg of egg protein.

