4.3.2.10 Laboratory Assessments

The development of tolerance in immunotherapy is associated with several immunological changes, including decreases in egg-specific IgE levels with concomitant increases in IgG4 levels. Serum IgE to egg white, ovomucoid and ovalbumin will be performed at baseline screening (TS) and at the end of study (T3) for all subjects and additionally for active subjects who have a visit at T4.

Other than serum immunoglobins assay, 3 mL of Ethylenediaminetetraacetic acid anti-coagulated blood will be concurrently collected (TS, T3 and if applicable, T4) and sent to a core laboratory for peripheral blood mononuclear (PBMC) preparation. We expect 3 mL of blood to yield approximately 6 million PBMCs. These following experiments will be performed:

- i. DNA-human leukocyte antigen (HLA) genotypes: DNA will be isolated from 0.2 mL of blood to perform HLA typing to determine the appropriate candidates for major histocompatibility complex (MHC) tetramers analysis and genome sequencing if new data arises that indicates the importance of other non-HLA genetic variants for allergy manifestation.
- ii. Multi-parametric immune cell profiling: We will utilise multi-parametric cytometry to holistically characterise the immune system and determine the differences between non-responders and those with SU to identify immune signatures that confer resistance to OIT. Absolute counts of B, T, natural killer and dendritic cell subsets will be characterised.

- iii. Transcriptomic analysis: This will be done either at the immune cell subset or single cell level depending on the immune cell profiling data to identify the pathways responsible for the differences in response to OIT.
- iv. Multi-parametric cytokines/chemokines profiling: This will be done on the plasma stored after PBMC preparation if the cytometry data indicates the involvement of specific cytokines/chemokines in allergy manifestation.

4.3.3 Final Study Visit:

The final study visit will be on the day of DS challenge (T3) for controls and for active subjects who did not achieve desensitisation. The final study visit will be on the day of SU challenge (T4) for those successfully desensitised at T3.

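### Egg-specific IgE is measured in both arms at baseline and T3 but tested only within each arm, so no listed analysis separates an OIT effect on IgE from natural decline

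*Combined protocol and SAP*

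**What the plan says.** The last bullet of section 9.2.2 reads "Immunological outcome measures pre- and post- of OIT, using paired t test", with the alternative "or Wilcoxon signed rank test if normality assumption is not tenable) within each group". No other section adds an active-versus-control test for immunology. The one further contrast, in section 4.3.2.10, sets non-responders against those with sustained unresponsiveness, for immune-cell profiling.

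The other outcomes in section 9.2.2 (sustained unresponsiveness, adverse events, completion, quality of life) are compared between arms. The quality-of-life bullet directly above has paired tests and also a test of change "between the active and control groups using two independent sample t test".

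The IgE data for such a comparison are planned. Section 4.3.2.10 states: "Serum IgE to egg white, ovomucoid and ovalbumin will be performed at baseline screening (TS) and at the end of study (T3) for all subjects".

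Objective 3 in section 2.3 is "To compare immunological outcomes (skin prick test to egg white, serum IgE to egg white, ovomucoid, ovalbumin) at baseline and end of OIT program". It names no contrast between arms. Section 1.2.2 says the control group "will be used to control for the incidence of natural resolution of egg allergy over the study period".

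On who reaches T3, section 4.3.2.6 says "All participants who have completed at least 16 weeks of maintenance pancake OIT (Table 5 Step 7) will undergo an open cooked egg challenge" for the active arm and "All control subjects will undergo an open cooked egg challenge between 12 and 18 months (T3" for controls. Under section 4.4.2, blood after withdrawal is taken at a discontinuation visit if the subject is willing.

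**The concern.** Egg allergy can resolve without treatment; section 9.1 assumes about 15% over 12 months. Section 4.3.2.10 links tolerance under immunotherapy to falling egg-specific IgE. A fall in the active arm could therefore come from OIT, from natural decline, or from both, and a paired test within that arm cannot divide them. The concurrent control arm can, but no listed analysis uses it for IgE.

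Setting one arm's p-value beside the other's does not fill the gap. With 2:1 allocation the active arm has twice the subjects, so for the same true fall it reaches p < 0.05 more often. What is at stake is the interpretation of one secondary outcome.

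**Working it through.** The documents give no power, SD, correlation or rate of decline for IgE, so there is no stated figure to reproduce. Those inputs are assumed and shown as ranges.

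**Inputs from the documents (section 9.1):** 22 active and 11 control; two-sided 0.05; 30% attrition. 22 × 0.7 = 15.4 and 11 × 0.7 = 7.7, taken as 15 and 8.

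**Step 1. Equal decline in both arms, no OIT effect.** Let δ be the mean fall divided by the SD of change. For n subjects the paired t statistic is noncentral t with n − 1 df and noncentrality δ√n. With independent arms,

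P(active only) = P(active significant) × [1 − P(control significant)].

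| δ (assumed) | 22/11: active, control | Active only | 15/8: active, control | Active only |
|---|---|---|---|---|
| 0.1 | 7.3%, 6.0% | 7% | 6.5%, 5.7% | 6% |
| 0.25 | 20.1%, 11.7% | 18% | 14.7%, 9.4% | 13% |
| 0.5 | 60.9%, 32.3% | 41% | 43.8%, 23.2% | 34% |
| 1.0 | 99.4%, 84.8% | 15% | 94.9%, 68.1% | 30% |

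Example at 22/11 and δ = 0.5: 0.609 × (1 − 0.323) = 0.412. The reverse pattern, control only, has probability 0.323 × (1 − 0.609) = 0.126, so the asymmetry follows the arm sizes. The active-only rate peaks at 43% near δ = 0.58 (22/11) and at 43% near δ = 0.72 (15/8).

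**Step 2. A direct between-arm test under the same null.** Simulation used bivariate normal log IgE with equal SDs and baseline/follow-up correlation r = 0.5 or 0.8 (assumed). Rejection rates were 5.0% to 5.2% for ANCOVA, 4.9% to 5.2% for a t test of change and 4.6% to 5.0% for Mann-Whitney on change. These rates are per marker. For three independent markers, the chance of at least one false positive would be 1 − 0.95³ = 14%. Minimisation was not modelled.

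**Step 3. Power of a between-arm test.** The effect is an extra active-arm fall in baseline SDs; each range runs from r = 0.5 to r = 0.8.

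| Effect, arm sizes | ANCOVA | t test of change | Mann-Whitney |
|---|---|---|---|
| 0.5 SD, 22/11 | 32% to 58% | 26% to 54% | 24% to 52% |
| 0.5 SD, 15/8 | 23% to 42% | 19% to 40% | 18% to 38% |
| 1 SD, 22/11 | 85% to 99% | 75% to 98% | 72% to 98% |
| 1 SD, 15/8 | 68% to 94% | 58% to 93% | 55% to 91% |

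The mean half-width of the ANCOVA 95% CI is 0.66 to 0.46 baseline SD at 22/11 and 0.80 to 0.56 at 15/8. As a check by formula at 22/11 with r = 0.5: residual SD = √(1 − 0.25) = 0.866, √(1/22 + 1/11) = 0.369, t(30 df) = 2.042, and the product is 0.65.

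**Step 4. Selectively missing T3 samples.** Assume that 15 of 22 active subjects are observed, controls (11 or 8) are missing at random if at all, and OIT has no effect. If completing correlates 0.3 to 0.5 with a larger IgE fall, ANCOVA is biased by 0.09 to 0.22 baseline SD in favour of OIT and rejects in 7% to 10%. If completing depends only on baseline IgE, ANCOVA is unbiased (4.9% to 5.2%).

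**The case against.** The strongest reply is that the plan answers the question it sets. Objective 3 asks for baseline against end of programme, and paired tests do that. This stands: there is no contradiction between objective and analysis, and the paired tests need not be removed or downgraded.

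A reader might infer that the plan carries a false-positive rate of around 40% for IgE. The documents do not support that. Nowhere do they propose reading two within-arm p-values as a difference, and a significant active-arm result under a real decline is a correct detection of change. The rates in Step 1 describe a misreading that the plan leaves open, and they depend on an assumed decline.

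A reader might also infer that the control arm was included to adjust IgE. Section 1.2.2 speaks of resolution of egg allergy, a clinical outcome, which the between-arm Fisher test in section 9.2.1 addresses. The argument here is only that the same arm can serve for IgE at no extra sampling.

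Three cautions about the remedy also stand. The 5% error is per marker, so a lead marker should be named. An ANCOVA on baseline IgE leaves out the other two minimisation factors in section 4.1 (age and asthma on inhaled corticosteroids). Discontinuation samples are taken at varying times and do not belong in the main T3 model. Low power is a fair comment too, but it favours reporting an estimate with its interval; the within-arm tests do not address the between-arm question at all.

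**Conclusion.** The point holds as a gap in inference on a secondary outcome. As listed, the analyses can show that egg-specific IgE changed in an arm but not that OIT changed it more than avoidance did, even though the samples for that comparison are planned in both arms. The gap lies in the listed tests and not in the design, which allows the comparison.

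If the within-arm results were misread as a contrast, the misleading pattern would arise in about 7% to 43% of trials at 22/11 and 6% to 43% at 15/8, for assumed declines of 0.1 to 1.0 SD of change. A direct test holds the error near 5% per marker. Its ANCOVA power is about 23% to 58% for an assumed 0.5 baseline SD effect and 68% to 99% for 1 SD, across both sample sizes and r = 0.5 to 0.8. Selectively missing active-arm T3 samples could still bias it. The point is confined to serum IgE, where collection in both arms is explicit. The primary conclusion is not affected.

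**What to change.** Keep the paired tests and Objective 3 as they are, and add to the immunology bullet in section 9.2.2:

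> T3 serum egg-white IgE (lead marker), and ovomucoid and ovalbumin IgE (supportive), will be compared between randomised arms by ANCOVA of log IgE on arm and baseline log IgE, reported as the geometric-mean ratio (active/control) with 95% CI. If normality is not tenable, a Mann-Whitney U test of the change in log IgE is used. The main analysis uses T3 samples. Discontinuation-visit samples are added only in a sensitivity analysis. The number in each arm without T3 IgE is reported.

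If the sponsor prefers the smallest change, extending the quality-of-life bullet's between-arm test of change to IgE would also close the gap, with somewhat less power.

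The cost is a few sentences of SAP text and a few lines of SAS, with no new assay. The practical effort is obtaining T3 blood from active subjects who do not reach the T3 challenge, which section 4.3.2.10 already calls for by specifying T3 IgE for all subjects.
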